Recruitment. A two-stage detection method will be utilized to identify a sample of PTSD treatment seekers. Based on our previous study, we expect a 15% drop-out rate prior to the start of intervention; these will be replaced. Subjects who withdraw after starting treatment will not be replaced: based on our previous study we expect a 10% rate. This would leave 40 in each intervention group for a treatment completion analysis. Data of subjects who withdraw at any time after randomization will be retained for intent-to-treat analyses.

Stage I: Screening for Inclusion/Exclusion. The PM/RA will contact potential subjects and ask them to provide written informed consent for study screening. Those who consent will be assessed with screening questions for inclusion and exclusion criteria, availability, and willingness to participate in the study. This visit may be conducted in person or by phone and will take about 20 minutes.

Stage II: Inclusion Confirmation. The assessor will administer The CAPS-5, a modified Structured Clinical Interview for Diagnosis DSM-5 (SCID-5, now modified) (First et al, 2001), and the Dissociative Experiences Scale-II (Bernstein & Putnam, 1985) to assess inclusion and exclusions and further assess willingness and capacity to participate (i.e., have time and motivation). The Deployment Risk and Resiliency Inventory (DRRI) combat experiences scale and preparedness scale (Vogt et al, 2008) will be administered to aid group allocation. The study PI will assess current medications as potential exclusions. This visit will take about 2 to 3 hours.

After confirmed inclusion, the PM will reiterate the schedule, group allocation and compensation, and obtain written informed consent for participation. This will include informed consent to be videotaped to assess treatment fidelity. All hard and electronic data forms will be identified only by SID#. The clinical assessor will assess participants at each time point blind to group allocation. This procedure will keep the assessor blind to intervention allocation, and investigators and clinicians blind to assessment data to minimize performance and outcome detection bias.

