Group 1: Verum acupuncture (ACU). Individual treatment sessions are 1 hour twice per week for 12 weeks, and reflect clinical practice with an interview (10 minutes), pulse and tongue observation (5 minutes), standard needling, and needle retention (30 minutes). Subjects receive a standard acupuncture point prescription defined in our previous study and chosen for the most likely TCM diagnostic patterns for PTSD. An alternating by session front and back treatment will be used to avoid point fatigue (tolerance due to frequent use). The front treatment is comprised of 11 needles, bilaterally at LV3, PC6, HT7, ST36, SP6, and at the single Yintang point; the back treatment is 14 needles, bilaterally at GB20, and UB14, 15, 18, 20, 21, and 23. In addition to the standard points, three additional points (chosen from a list of 15 points) will be chosen to address a subject's constitution based on the TCM diagnostic patterns. A complete description of the experimental intervention is provided in published reports ([name] et al, 2007; Sinclair-Lian et al, 2006) ([PMID: 17568299](#) and [16494568](#)).

Group 2: Sham acupuncture: minimal needling (MIN). Individual treatment sessions are 1 hour twice per week for 12 weeks. Three elements define minimal needling in this study. The first is the location of the needles, which are 2 cm lateral or medial to actual points, which are not associated with PTSD (Sinclair-Lian et al, 2006) and are not expected to effect PTSD symptoms. The second is the insertion depth, which will be superficial (<0.25 inch) in MIN compared to verum. The third is the relative absence of stimulation, although there will be a non-functioning stimulator used to complete the sham effect. The acupuncturist will ensure that no DeQi sensation is obtained. The protocol uses 11 front and 14 back points for the sham acupuncture group (MIN) to match the number and body position (alternating prone and supine) of points in the verum acupuncture group (ACU).

Compensation Plan. Subjects will be compensated for their time and travel to participate in the study. Subjects will be compensated \$25 each for initial and post-treatment assessment, \$50 for each of 3 biological assessments, and \$50 for completing the intervention for a total possible compensation of \$250 per subject.

Protection of Human Subjects: See Human Subjects Detail

III. Data Management

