General Approach. General linear mixed models (GLMM) are capable of handling multiple underlying distribution and model structures through link functions, such as repeated measures random effects models of continuous outcomes (identity link), repeated measures logistic models (logit link), and Poisson and negative binomial models (log link). In addition to modeling global fixed effects across subjects, GLMM can also model individual subject random effects. Survival analysis allows for the assessment of time to event modeling using probability estimates on survivor functions and estimates of hazard ratios. Time to event modeling using Cox proportional hazard modeling allows for all subjects to contribute information to the model up until occurrence of event, drop out, or end of study. Cox Proportional Hazards modeling will be used to investigate for effect-size of the treatment by allowing subjects to contribute their information to the model while they are being observed and censored once they are no longer being observed (loss to follow-up or end of study period). Further, using the Cox modeling we will investigate for time dependencies and informative loss to follow-up. In the case where dropouts may be associated with the treatment assignments, we will leverage intention to treat methodology and construct a piecewise random effects model with both "on-" and "off-treatment" slopes. GLMM will be used to evaluate the primary clinical hypothesized effects of treatment (ACU) on the clinical outcome of PTSD symptom severity (CAPS) over time (mid- and end-treatment, and 1-month follow-up), controlling for baseline severity of symptoms and demographic characteristics (e.g., age, gender) in comparison with placebo control group (MIN) with assumption of intent to treat. Cohen's *d* within and between subjects will be calculated. Interaction terms will be included in the models to evaluate treatment fidelity and treatment expectancy as potential moderators.

GLMM will also be used to evaluate the secondary biological hypothesized effects of treatment on pre- to post-treatment in PPR (decreased EMG eyeblink). These same statistical procedures (GLMM, survival analysis, and Cohen's *d* with intent to treat) will be applied to evaluate exploratory outcomes: clinical symptoms comorbid with PTSD, PPR (HR, HRV, SCR), and PTSD diagnosis.

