Controlling for non-specific treatment-related effects. In this study, it is critical for those in the control group (MIN) to receive an equivalent amount and kind of time, empathy, setting, and assessment as those in the verum acupuncture group (ACU). Both verum and control protocols will include language currently in our acupuncture clinical trials manual for greeting, interacting with, and closing a session. Prior to the first session, each subject will meet with the acupuncturist who will conduct a Traditional Chinese Medicine (TCM) diagnostic session. A protocol example from our first acupuncture for PTSD study is Appendix A to this Attachment and included pragmatics and acupuncturist behavior. Note that this example differs in content from the proposed study. On funding, a protocol manual will be developed.

Outline of Steps of Procedures and Interventions

Step one: Conduct informed consent and conduct pre-treatment evaluation

Protocol Rev 3. 4.10.2018 MH

Step two: Randomization to group

Subjects will be allocated to group by adaptive randomization.

Step three: Begin and continue ACU or MIN interventions

Step four: After 12-week intervention, stop ACU and MIN and conduct End-Treatment Assessments

Step six: At the end of follow-up period (planned one month), determine how and where to transition subject to clinical care

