Note: One task of Data Safety and Monitoring on funding will be to review the protocol and advise the investigators about rules for continuation or discontinuation of each subject in the study and in the follow-up period. It may be unethical to continue Veterans in the follow-up period if there is no pre- to post-treatment reduction in CAPS. Furthermore, we are most interested in whether there is effect maintenance in those who have responded to treatment, so it may be scientifically meaningless in addition to the ethical dilemma to continue non-responders into the follow-up period. In this A1 revision, our primary goal is to determine if ACU provided effect (signal) compared to a placebo, and the follow-up period is not to primarily determine durability of treatment but to ensure safety and clinical follow-up planning. Our statistical methods will be able to manage data in an intent-to-treat model if subjects are withdrawn. Our current plan is to define a response as a CAPS-IV equivalent drop of 10 points (the value for CAPS-5 still needs to be determined). Those who have not had a response would have the option to withdraw and re-initiate clinical treatment immediately. Of course, any subject may withdraw at any time.

Description of Intervention Protocols

Recruitment of participants currently on medications for PTSD. It may be ideal to recruit subjects who are medication naïve, but this is not feasible in this single site study. Approximately 55% of Veterans with PTSD who are entering three of our current studies (a DoD funded multi-site trial of prolonged exposure with vs without virtual reality, [name] PI, [name], Long Beach site PI; a VA national cooperative studies program comparing prolonged exposure to cognitive processing therapy – CSP #591, [name] et al PI's, [name] Long Beach site PI and executive committee member; an industry sponsored two-site RCT of Vilazodone vs. placebo for PTSD, [name] and [name] Co-PI's) are on a medication when entering the trial, most often an SSRI. In the first two mentioned studies, the subjects can stay on the medication (with rules), and for the third study we offer a wash-out if the current medication has not been established for a long period or if effects are neutral or negative. We will thus offer a similar procedure in the proposed study to the first two mentioned studies, and the subject must be on a stable dose for 8 weeks or longer.

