Adverse effects are extremely rare when acupuncture is performed in a professional setting by a fully trained and certified acupuncturist. Four out of the 5 deaths that have been associated with acupuncture in the literature were not equivocally due to acupuncture or were either self administered or administered by an untrained person. Possibilities of cross-infection will be avoided by using disposable needles and following clean-needle technique procedures. Other adverse effects will be avoided by using a fully trained and licensed acupuncturist who will practice in a professional setting.

The risk of non-effectiveness is mitigated by subjects being allowed to be taking medications for symptoms of PTSD and related conditions. Participants will be seen twice per week for protocol, and will be assessed each visit for aggression and suicidal ideation. Rules for withdrawal from study because of symptoms and/or potential danger to self or others will be part of protocol.

The video tapes will be destroyed after they have been reviewed for treatment fidelity.

Any adverse events will be documented and reported to proper authority. All research staff has been or will be trained in and abide by ethical research methods and good clinical practices.

3. Potential Benefits

There may be no direct benefit for a person to participate in this study, although we hypothesize benefit to subjects in the ACU group. The risks are minimal but present. For this study, an emphasis on informed consent

and safety is important. Results from this study are intended to provide a better understanding of the effects of acupuncture on PTSD and on peripheral psychophysiology. This information may enhance knowledge of and shape the treatment for PTSD which may potentially help thousands of veterans suffering from this illness.

4. Importance of Knowledge to be Gained

This study will improve knowledge about the use of acupuncture for PTSD, and will inform the field and policy makers about how acupuncture may be useful treatment for symptoms and biological functioning. Research evaluating how abnormal biological function in PTSD might be reversible with intervention is rare, and this study will help us understand what is reversible and what is not. This may improve our knowledge about mechanisms of treatment, and perhaps provide insight into risk factors. This will hopefully provide potential biological targets for further study.

5. Data and Safety Monitoring

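### The fallback model for arm-related dropout needs CAPS-5 scores taken after a subject stops early, and the documents do not provide for collecting them

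*Protocol*

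**What the plan says.** The General Approach paragraph is the same in the protocol (section IV) and the SAP. For dropout that may be associated with assigned treatment it says "we will leverage intention to treat methodology and construct a piecewise random effects model", with one slope for time on treatment and one for time off it. The primary mixed model uses CAPS-5 at mid-treatment, end of treatment and 1-month follow-up, adjusted for baseline.

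Four other places in the protocol bear on which scores will exist:

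- Section III, Recruitment: "Data of subjects who withdraw at any time after randomization will be retained for intent-to-treat analyses". It expects 10% to withdraw after starting treatment, does not replace them, and counts 40 per group for a completion analysis.
- Section IV, Sample size needed and power: 10% attrition after randomisation takes 45 per group to about 40.
- Outline of Steps of Procedures and Interventions: "Step four: After 12-week intervention, stop ACU and MIN and conduct End-Treatment Assessments".
- The note after that outline, on subjects without a response at the end of treatment: "Those who have not had a response would have the option to withdraw and re-initiate clinical treatment immediately".

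The schedule in Assessment Detail names its CAPS-5 columns by treatment phase (mid, end) and by follow-up month. It gives no weeks from randomisation.

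**The concern.** An off-treatment slope for people who stop early has to be learned from scores taken after they stop. The documents keep the data of subjects who withdraw, but they do not say that a subject who gives up sessions is still assessed at the remaining visits. They also do not treat stopping sessions and leaving the study as different events. A site therefore has no instruction to collect the scores that the fallback model needs.

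The only off-treatment interval that the plan clearly provides is the month after the 12-week course. The people seen then have finished treatment, and non-responders may already have left. A slope from that group need not describe someone who stopped after a few weeks. If it is applied to dropouts, the analysis carries the intent-to-treat name while much of its information about dropouts comes from time on treatment. Scores that are never collected cannot be recovered at the analysis stage.

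**Working it through.** **Inputs from the documents.** Difference 8.5 and pooled SD 14.4; planning means 50 to 25 (ACU) and 50 to 33.5 (MIN); two-sided alpha 0.05, power 80%; 45 per arm; 10% dropout after start.

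**Assumed, because the documents do not give them.** Mid-treatment CAPS-5 at week 6, 1-month visit at week 16, example stopping times of week 4 and week 8, dropouts' final scores, and unequal dropout splits.

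**1. The plan's own figure.** Total N = 4 × [14.4 × (1.960 + 0.842) / 8.5]² = 90.1, or 92 if each arm is rounded up. The stated 90 reproduces. Power is 79.95% at 45 per arm and 75.2% at 40. Expected dropouts: 90 × 0.10 = 9. Remaining per arm: 45 × 0.90 = 40.5, in line with the plan's 40.

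**2. Where the off-treatment slope gets its information.** For a subject who stops at week T, the row at week t is (1, min(t, T), max(0, t − T)). The off-treatment slope is informed only if the third entry is non-zero at some visit.

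| Subject | CAPS-5 at weeks | Off-treatment weeks | Rank |
|---|---|---|---|
| Completer, attends 1 month | 0, 6, 12, 16 | 0, 0, 0, 4 | 3 |
| Completer, leaves before 1 month | 0, 6, 12 | 0, 0, 0 | 2 |
| Stops week 8, no later visits | 0, 6 | 0, 0 | 2 |
| Stops week 4, no later visits | 0 | 0 | 1 |
| Stops week 8, visits kept | 0, 6, 12, 16 | 0, 0, 4, 8 | 3 |
| Stops week 4, visits kept | 0, 6, 12, 16 | 0, 2, 8, 12 | 3 |

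Without later visits, only completers seen at 1 month inform the off-treatment slope. The week-4 dropout adds no post-baseline outcome at all when baseline is a covariate. With visits kept, dropouts inform the slope themselves.

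**3. Illustration of size.** Suppose every dropout ends at the baseline mean of 50. Then

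intent-to-treat difference = [33.5 + p(MIN) × 16.5] − [25 + p(ACU) × 25].

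- 10% in each arm: 35.15 − 27.50 = 7.65, a shift of 0.85 from 8.5.
- 16% ACU, 4% MIN: 34.16 − 29.00 = 5.16, a shift of 3.34.
- 4% ACU, 16% MIN: 36.14 − 26.00 = 10.14, a shift of 1.64 the other way.

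Both unequal splits keep the total at 9 (45 × 0.16 + 45 × 0.04 = 9). For scale, the standard error of the difference is 14.4 × √(2/45) = 3.04, so the shifts are about 0.28, 1.10 and 0.54 standard errors.

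**The case against.** The strongest reply is that the documents are silent and do not exclude these visits. Nothing makes the CAPS-5 schedule depend on staying in treatment, the step outline describes the ordinary course, and setting a completion analysis beside intent-to-treat fits with following non-completers. This stands as far as it goes: a reader might infer that visits end when sessions end, but no sentence says so. The gap remains, because no instruction provides for the visits and the sample-size text counts dropouts as reducing the numbers.

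The plan also commits to investigating informative loss to follow-up, and the piecewise model is only a contingency. Both are true, but investigating the loss does not supply the missing scores.

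Four stronger inferences are tempting and are not supported:

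- That the piecewise model cannot be fitted. It can be fitted overall, because completers have a 1-month score. The weakness lies in whose data identify the slope.
- That observation formally stops at dropout. The sentences that suggest this describe Cox time-to-event modelling and do not set rules for collecting CAPS-5.
- That those doing worst lose their endpoint. Protections Against Risk says only "Rules for withdrawal from study because of symptoms and/or potential danger to self or others will be part of protocol", and those rules are not in the document.
- That payment discourages end assessments. The protocol's first Compensation Plan pays the post-treatment assessment separately from completing the intervention.

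On size, a mixed model uses a dropout's own mid-treatment score where there is one, so it would not simply return 8.5. With equal dropout the shift is small beside the standard error, and the contingency might not be triggered.

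**Conclusion.** The point holds as a gap in data collection. The plan relies on off-treatment slopes if dropout is related to arm, but it does not provide for CAPS-5 after early stopping, and it lets non-responders leave before the one visit that is off treatment for everyone who attends. Without further visits, the slope applied to dropouts comes from selected completers, and the intent-to-treat estimate leans on on-treatment data.

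The size is uncertain. About 9 subjects are expected to be affected. The figures of 7.65, 5.16 and 10.14 rest on return to baseline, and the last two also on assumed splits. A reader might take them as limits, but they are not: a 20% ACU and 0% MIN split gives 25 × 0.80 − 16.5 = 3.5, and the protocol's Research risk paragraph allows that symptoms may get worse. What they show is that the direction and size of the shift depend on which arm loses more subjects, and arm-related dropout is the situation the fallback model is meant for. It should be corrected, because the change is small and later analysis cannot replace scores that were not taken.

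**What to change.** In the protocol, and by reference in the SAP:

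- Define stopping treatment and withdrawing from data collection as separate events.
- For every randomised subject who stops sessions early, and for end-of-treatment non-responders, keep the mid-treatment, week-12 and 1-month CAPS-5 at calendar times from randomisation, done by the blinded assessor, unless the subject declines. State the week of the mid-treatment visit.
- Record the date of stopping and the reason.
- Let a subject decline psychophysiology testing without leaving the CAPS-5 schedule. The protocol's Potential risks paragraph notes that participants in other studies did not want to return for it.
- Use these scores in the primary intent-to-treat model and to estimate the off-treatment slopes.
- Reconcile the 6-month column in the assessment schedule with the Data Management text, which plans no 6-month follow-up, because such a visit would be a further off-treatment time point.

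This concerns outcome assessment only. It leaves untouched who may stop treatment or return to clinical care. Scores taken after stopping will include the effect of any care restarted, which an intent-to-treat comparison accepts.

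The cost is protocol and consent wording and some added follow-up effort for about 9 expected dropouts, plus any non-responders who would otherwise have left before the 1-month visit.

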Data collection. The program manager (PM) will track recruitment and retention. A clinical assessor will conduct diagnostic interviews and questionnaire evaluations pre-, mid-, and post-intervention blind to group allocation. All pre-, mid-, and post-treatment biological measures will be conducted and analyzed by the psychophysiological and consultants, blind to group allocation.

Assessment, Data Collection, and Schedule. Instruments and other data collection tools and their description are in the [Assessment Detail](#). This strategy includes repeat measures yet minimizes response burden. Our goal is to test for effect signal. It is premature to evaluate durability and not ethical to keep subjects in a protocol where they may not be receiving effective treatment (particularly true of MIN), so we will not include a six-month follow-up period. Instead, a one-month follow-up will test symptoms and functioning and be utilized to re-connect participants to clinical services. Data collection at mid-point of treatment is warranted to replicate mid-treatment findings from our first trial. Such a finding may help determine dose effects and plan a dose-finding trial.

Outcome measures. The primary outcome is change in PTSD symptom severity from pre- to post-treatment. We hypothesize a large pre- to post-treatment effect for ACU ($d \geq 0.8$) and at least a mild treatment effect ($d \geq 0.30$) of the difference between groups (ACU vs MIN) pre- to post-treatment, with 80% probability of detecting a true group difference at $p < 0.05$ (2-sided). Main biological outcome (secondary outcome) is change from pre- to post-treatment in PPR (decreased startle by EMG eyeblink).

IV. Statistical Plan and Data Analyses

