Statistical Analyses, Primary Hypothesis. Prior to the application of any statistical modeling, underlying assumptions and conditions will be examined. Univariate analyses, including tests of distribution assumptions, t-tests, and chi-square tests will be conducted to determine possible significant covariates to be included in further multivariable modeling as well as to investigate efficiency of randomization techniques. All models will be assessed for goodness of fit as well as other diagnostics including assessment for collinearity performed on all covariates chosen for subsequent analyses. Repeated measures analysis of variance will be used to formally test the null hypothesis of no differences in baseline PTSD symptom mean levels and subsequent retest of PTSD symptom mean levels while simultaneously adjusting for any significant covariates. All models will be run accounting for any potential confounders. Analyses will be performed assuming intent to treat and informative loss-to-follow up will be investigated. Additional analyses will be conducted to determine interactions and mediating effects while simultaneously adjusting for other covariates in the model.

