Effects. The conservative assumptions noted above will result in pre- to post-treatment Cohen’s $d = 2.07$ within group (ACU) and between group (post-treatment difference) Cohen’s $d = 0.59$, which will prove the null hypothesis false and show a large treatment effect for ACU and a moderate between-group effect size.

Sample size needed and power. The conservative assumptions would require a total of 90 patients in a two-treatment parallel-design to provide a probability of 80 percent to detect a treatment difference at a two-sided 0.05 significance level. Modest assumptions of a 12-point difference with a pooled SD of 15 requires a total of 50 patients with power of 0.80 at $\alpha < 0.05$.

This was determined using a formula for a random effects modeling (Montgomery, 1991), which may determine the necessary sample size to detect a statistically significant difference in treatment/control group means at different levels of projected effect differences.

$$n = \frac{2 * a * M^2 * \Phi^{*2}}{\Delta^2}$$

Where:

M = measure of noncentrality parameter to estimate the standard normal probability of making a type II error

n = number of replicates necessary for each treatment

a = number of treatments (a=2)

Φ^* = estimated standard deviation

Δ = difference in baseline and post treatment

Table. Examples of sample sizes necessary for significance testing at different mean and SD’s (between group: treatment (ACU) and control (MIN)) for PTSD severity (primary outcome) at power = 0.80.

Mean difference between ACU and MIN PTSD severity scores post-treatment	Φ^2	Total N Using Formula Above
8.5	12	62
	14.4	90
	15	96
	20	162
12	12	32
	15	50
	20	86

Recruitment goals are N=90, 45 per group. With a post-randomization attrition rate of 10% we will have at least 40 individuals in each group. Considering attrition, the above table indicates that for an average difference in means of 12 at end-treatment with a standard deviation of 15, a total sample size of 50 (25 in each group) would be more than adequate to report a statistical difference with 80% power. If differences in treatment group means were found to be larger than 12, we would need even fewer subjects in our treatment groups to achieve statistical significance.

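### Two unreconciled methods are named for the primary CAPS-5 hypothesis, and the one called the formal test (repeated measures ANOVA) would in its standard form drop withdrawals that the protocol promises to keep

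*Protocol*

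**What the plan says.** The protocol (section IV) and the SAP carry the same analysis text, and it names two methods for one hypothesis.

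- **General Approach:** "GLMM will be used to evaluate the primary clinical hypothesized effects of treatment (ACU) on the clinical outcome of PTSD symptom severity". The visits and adjustment are given as "mid- and end-treatment, and 1-month follow-up), controlling for baseline severity of symptoms". The analysis is intent-to-treat, and a piecewise random-effects model is held in reserve in case dropout is related to arm.
- **Statistical Analyses, Primary Hypothesis:** "Repeated measures analysis of variance will be used to formally test the null hypothesis of no differences in baseline PTSD symptom mean levels", together with a later retest of those means and covariate adjustment. The section does not list the visits in the ANOVA and gives no rule for a missing visit. It adds that analyses assume intent to treat and that informative loss will be investigated.

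Four other protocol statements bear on this:

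- **Endpoint** (Outcome measures): "The primary outcome is change in PTSD symptom severity from pre- to post-treatment".
- **Population** (Recruitment): "Data of subjects who withdraw at any time after randomization will be retained for intent-to-treat analyses". The same paragraph reserves the 40 per arm for a separate completion analysis.
- **Expected loss** (Recruitment): "Subjects who withdraw after starting treatment will not be replaced: based on our previous study we expect a 10% rate". The sample size section adds: "With a post-randomization attrition rate of 10% we will have at least 40 individuals in each group".
- **Follow-up** (note in Clinical Protocol Detail, after the outline of steps): "Those who have not had a response would have the option to withdraw and re-initiate clinical treatment immediately". The note describes a current plan for the follow-up period, leaves the CAPS-5 response threshold undetermined, and says the statistical methods can accommodate withdrawn subjects under intent to treat.

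**The concern.** A mixed model fitted by likelihood uses whatever scores a subject has. Repeated measures ANOVA in its standard form needs a score at every modelled visit and otherwise removes the subject, including scores that were collected. An analyst who takes the primary-hypothesis section literally would therefore run a completer analysis as the formal test, contrary to the intent-to-treat commitment. An analyst who takes General Approach literally would run something else. The two can disagree, and nothing in either document settles which result stands.

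At stake are the analysis population of the primary test, some power, and the freedom to choose between two results after the data are seen.

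**Working it through.** **1. Reproduce the plan's sample size.** Inputs from the power section: difference 8.5, SD 14.4, two-sided 0.05, power 80%.

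Total N = 4 × 14.4² × (1.960 + 0.842)² / 8.5² = 90.1, against the stated 90. At 45 per arm the normal-approximation power is 79.95% (t-test 79.1%). The stated figure reproduces and assumes 90 scored subjects.

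**2. Apply the plan's own attrition.** 10% of 90 is 9 subjects; 45 × 0.9 = 40.5, which the plan takes as 40 per arm. Power = Φ(d × √(n/2) − 1.960).

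| Assumption | n per arm | d × √(n/2) | Power, normal | Power, t-test |
|---|---|---|---|---|
| 8.5 / 14.4 (d = 0.59) | 45 | 2.80 | 80.0% | 79.1% |
| 8.5 / 14.4 | 40 | 2.64 | 75.2% | 74.1% |
| 12 / 15 (d = 0.80) | 45 | 3.79 | 96.7% | 96.4% |
| 12 / 15 | 40 | 3.58 | 94.7% | 94.2% |

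This needs only baseline and end of treatment in the ANOVA. Not all of the loss is due to the method: a subject with no end-of-treatment score contributes to a mixed model only through other visits, chiefly mid-treatment.

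**3. Conditional scenario: the follow-up exit.** This step applies only if the ANOVA includes the one-month visit. A non-responder who leaves follow-up then has no one-month score and is deleted, although the end-of-treatment score was observed.

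From the documents: baseline 50 (SD 10), end 25 (13.8) for ACU and 33.5 (15) for MIN. Assumed, because the documents give no figure: baseline-to-end correlation r of 0.3 to 0.5, a CAPS-5 response cut of 6 to 10 points, and half or all of the non-responders leaving.

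SD of change = √(10² + SD_end² − 2 × r × 10 × SD_end). Non-responder share = Φ((cut − mean change) / SD of change).

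| r | Cut | SD of change, ACU / MIN | Non-responders, ACU | Non-responders, MIN |
|---|---|---|---|---|
| 0.3 | 6 | 14.41 / 15.33 | 9.4% | 24.7% |
| 0.3 | 10 | 14.41 / 15.33 | 14.9% | 33.6% |
| 0.5 | 6 | 12.35 / 13.23 | 6.2% | 21.4% |
| 0.5 | 10 | 12.35 / 13.23 | 11.2% | 31.2% |

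If all leave, the mean change among those remaining is μ + σ × φ(a) / (1 − Φ(a)), with a = (cut − μ) / σ.

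- r = 0.3, cut 10: ACU 25 + 14.41 × 0.2321/0.851 = 28.9; MIN 16.5 + 15.33 × 0.3646/0.664 = 24.9; difference 4.0.
- r = 0.5, cut 6: ACU 25 + 12.35 × 0.1221/0.938 = 26.6; MIN 16.5 + 13.23 × 0.2911/0.786 = 21.4; difference 5.2.

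Simulation agrees: 4.0 to 5.2 points if all leave and about 7 points if half leave, instead of 8.5. A t-test on change, starting from 40 per arm, has 71–84% power with no exit, about 55–71% if half leave and about 27–53% if all leave. The no-exit range differs from step 2 because the SD of change depends on r. This is a simple comparison of change scores that shows the direction and rough size of the selection; it is not the power of a four-visit ANOVA.

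**4. Which method fits the exit mechanism.** The exit depends on the pre- to post-treatment CAPS-5 change, which is recorded. Missing one-month scores would then be missing at random given the modelled data, which a likelihood mixed model accommodates and complete-case deletion does not.

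**The case against.** The strongest reply is that the plan already provides an intent-to-treat mixed model for the primary CAPS effect, a fallback model for treatment-related dropout, and general statements that analyses are intent-to-treat and that withdrawn subjects can be handled. A reader might infer from the ANOVA sentence that the plan can run only on complete cases. The documents do not support that; the mixed model is plainly there. What remains is that the formal test is assigned to the ANOVA in the section headed for the primary hypothesis, the mixed model is assigned under general approach, and no sentence ranks them. The general statements assert a property that standard repeated measures ANOVA lacks and give no rule for a missing visit. If the authors meant a mixed model by that label, one sentence would settle it, but neither document contains it.

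A reader might also infer that non-responders leave before the primary endpoint is measured. They do not. The option concerns the follow-up period, is tentative, and turns on the post-treatment score, so the primary endpoint has already been collected. If the ANOVA stops at end of treatment, this exit removes nobody. The visit list that includes one month belongs to the mixed model; the ANOVA sentence lists none.

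Finally, the loss on the plan's own figures is modest, and at the 12-point assumption it hardly matters. That is correct.

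**Conclusion.** The concern holds as an inconsistency between two named primary methods, with no missing-visit rule for the one called the formal test. In its standard form that test conflicts with the commitment to keep withdrawals in the intent-to-treat analysis.

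The size that rests on the plan's own numbers is about 9 of 90 subjects and a fall from about 80% to 74–75% power at 8.5/14.4, only part of which a mixed model would recover. The direction of any bias from ordinary withdrawal cannot be told from the documents.

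The drop to about 7 points, or 4 to 5 points, is conditional. It needs the one-month visit in the ANOVA, deletion of incomplete subjects, the assumed response cut and correlation, and half or all non-responders taking an optional exit. The all-leave case is an upper bound, not a forecast. In that scenario deletion falls more heavily on MIN and understates the benefit of ACU.

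**What to change.** In the primary-hypothesis section of both documents:

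- Make the likelihood-based mixed model from General Approach the single formal primary analysis, with arm, visit, arm-by-visit and baseline CAPS-5. Take the test from the ACU–MIN contrast at end of treatment, which matches the stated endpoint.
- Use every observed CAPS-5 score from every randomised subject. Placing baseline in the response vector, for example, keeps subjects who have no post-baseline score.
- State the missing-at-random assumption and add one sensitivity analysis for departures from it.
- Delete the repeated measures ANOVA or label it supportive. Report complete cases only as the completion analysis foreseen under Recruitment.

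The cost is wording in two documents and one extra sensitivity analysis; no new visits, data or subjects are needed. The change should be made before unblinding, so that the choice of method cannot depend on the results.
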